Data Analysis: fMRI data preprocessing will be performed using methods previously described in our work.^{18,19} Briefly, ASL images will be combined into a single CBF volume, and motion will be corrected using filters designed to minimize perfusion-based fluctuations. After these corrections are performed, global CBF will be calculated as a voxel-wise mean from the CBF volume. All non-fMRI variables will be checked for normality, and any non-normal outcome measures will be log-transformed as appropriate. Sex is an important biological variable in chronic pain¹⁰⁹, and we will report data disaggregated by sex.

However, due to the overrepresentation of females in RA, we are not powered to test for sex differences. In addition, a priori covariates will include sex, race, medication classifiers, age, clinical pain severity, depression symptoms, and anxiety symptoms, as each has been linked to variation in RA symptoms and other rheumatic diseases.^{26,110,111} Missing data will be handled by restricted maximum likelihood. If the missing-at-random assumption is violated, multiple imputation will be considered. Two-tailed p values ($\alpha = .05$) with 95% confidence intervals will be used to evaluate statistical significance.

The functional image analysis package FSL (FMRIB Software Library, Oxford, UK) will be used for first and second level statistical analyses. Functional images derived from CBF volumes are concatenated into a 4D volume for each individual, smoothed, normalized, and coregistered onto structural images using a standard nonlinear transformation.^{112,113} Next, regional signal changes in a priori regions (lOFC, putamen, vmPFC, and NAc) are assessed in first level, with T/F statistic images Gaussianized and cluster thresholded to correct for multiple comparisons across brain voxels.¹¹⁴

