Mixed effects modeling will be used as the primary analytic strategy for the primary outcomes. In our group therapy RCT design, mixed effects models permit the modeling of cohort-level random effects, as well as heterogeneous variance/covariance matrices to account for potential alpha inflation due to cohort-level clustering. We will test regional signal change in each ROI using mixed effects models examining within-person main effects of thermal stimulus (HEAT; i.e., painful vs. warm) and skill practice (PRACTICE; i.e., rest vs. active practice in the scanner during delivery of thermal stimuli), and the between-person main effect of intervention condition (CONDITION; i.e., MB vs. Sham MB vs. SAV), as well as their requisite 2-way and 3-way interactions. Thus, the HEAT X PRACTICE X CONDITION interaction will test the extent to which CBF in each a priori corticostriatal region varies during the active practice of either Sham MB, or SAV, relative to rest. Planned comparisons will test each of the HEAT X PRACTICE 2-way interactions within intervention groups to aid in the interpretation of the 3-way interaction.

Updated Statistical Approach due to Covid-19

Due to COVID-19 restrictions, we had to drop one arm from the study (Mindful Breathing). As such, a new statistical analysis plan was developed that we detail in the next section.

fMRI Pre-Processing: Imaging analysis was conducted using Functional Magnetic Resonance Imaging of the Brain (FMRIB) Software Library (Center for FMRIB, University of Oxford, Oxford, UK) and ASL data processing toolbox. Five subjects were excluded from analysis due to detected image artifact or excessive motion. A total of 29 subjects (15 SAV group, 14 NMB) were included in the final imaging analysis. Subjects underwent 8 functional (ASL) runs during the MRI challenge session. The 8 ASL images that resulted from the runs represented combinations of two experimental conditions: Pain (nonpainful warm stimulus vs. noxious heat) and Practice (no meditation vs. meditation). These combinations occurred in the following order: 1. warm + no meditation; 2. noxious + no meditation; 3. warm + no meditation; 4. noxious + no meditation; 5. warm + meditation; 6. noxious + meditation; 7. warm + meditation; 8. noxious + meditation.

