ASL images were motion corrected using the ASL MRI MoCo Method (Wang 2012). An additional motion correction and signal outlier filtering step was included (Tan et al 2009) to account for excessive motion and corruptive signal fluctuations. ASL images were converted into absolute CBF units according to the general kinetic model. The 8 CBF images were concatenated, intensity normalized, and then smoothed with a 9mm full-width half maximum (FWHM) Gaussian kernel. The images were spatially normalized to the MNI (Montreal Neurologic Institute) standard space using a 12-parameter affine transformation and then a nonlinear transformation. Additionally, a global white matter value was calculated for each CBF image by

extracting average white matter values from FSL's MNI152 white matter mask. The global white matter value was included in statistical models as a nuisance regressor.

Statistical Approach for fMRI: A group one-sample t-test ($n = 29$) was used to determine whole-brain, pain-related regions. The two Warm+No Meditation scans were subtracted from the two Noxious+No Meditation scans and then averaged. This average residual value per subject was used as the dependent measure included in the one-sample t-test.

Multiple regression analyses investigated the relationship between pain intensity/unpleasantness ratings and CBF during the Noxious condition. The 1st regressor consisted of the mean difference between the 2 Noxious+no Meditation scans vs Noxious+Meditation scans. The 2nd regressor included the percent change in subjects' pain intensity ratings from the Noxious+no Meditation to the Noxious+Meditation scans. The 3rd regressor included the percent change in the subjects' pain unpleasantness ratings from the Noxious+no Meditation to the Noxious+Meditation scans. All 3 regressors were orthogonalized to each other.

Because this was a proof-of-concept pilot mechanistic trial with a limited sample size, we set voxelwise threshold to 2.3, cluster corrected at $p=0.05$ (Worsley et al., 1992), in line with previous meditation-based imaging studies of similar size (Zeidan et al., 2015).

d. Early stopping rules.

We will report all adverse events and evaluate on a case-by-case basis whether the occurrence of a particular adverse event has implications for discontinuing the study to ensure participant safety and well-being.

8. Risks

a. Medical risks, listing all procedures, their major and minor risks and expected frequency.

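### The Z > 2.3 cluster-forming threshold is justified by small sample size and precedent, and its 0.05 corrected level rests on an unchecked assumption about spatial autocorrelation

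*Combined protocol and SAP*

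**What the plan says.** The updated plan (section 7c, Statistical Approach for fMRI) sets one inference rule: "Because this was a proof-of-concept pilot mechanistic trial with a limited sample size, we set voxelwise threshold to 2.3, cluster corrected at" p = 0.05. It gives two reasons: the limited sample just quoted, and that the choice is "in line with previous meditation-based imaging studies of similar size". The rule closes a section that describes a whole-brain one-sample t-test of noxious minus warm scans without meditation, and multiple regressions relating CBF to changes in pain ratings. It is the only multiplicity control stated there.

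The Data Analysis part of 7c, written before the update, describes regional signal "with T/F statistic images Gaussianized and cluster thresholded to correct for multiple comparisons across brain voxels", without a threshold value.

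fMRI Pre-Processing says the images were "smoothed with a 9mm full-width half maximum (FWHM) Gaussian kernel". On the sample: "A total of 29 subjects (15 SAV group, 14 NMB) were included in the final imaging analysis".

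No section describes a check of the spatial autocorrelation, a permutation test, or a repeat at another cluster-forming threshold.

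**The concern.** A small sample lowers power. It does not make a low cluster-forming threshold more valid, and earlier use of that threshold shows custom rather than error control in these images.

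Random-field cluster p-values are calculated on the assumption that the noise autocorrelation is close to Gaussian in shape. At a low threshold, clusters are large, and their size under the null depends on correlation at longer distances. If the true autocorrelation has long tails, noise alone can form clusters larger than the formula expects, and the corrected 0.05 is exceeded. Smoothing with a Gaussian kernel does not remove such tails.

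The primary outcome is brain function in the corticostriatal circuits (7a). With 29 scans analysed, statements about which regions respond rest on which clusters survive this rule. The risk is naming regions that reflect noise while describing them as corrected at 0.05.

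**Working it through.** **Inputs from the documents.** Cluster-forming Z = 2.3; cluster-level p = 0.05; kernel 9 mm FWHM; n = 29; whole-brain search for the one-sample map.

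**Inputs assumed, because the documents do not give them.** Search volume (about 1.5 million mm³ in simulation B, 1,410 cm³ in A), noise autocorrelation before smoothing, one-directional testing, and Z = 3.1 as the stricter comparison.

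**1. What the rule demands.** The standard random-field approximation, with Λ the field's roughness matrix and F its FWHM:

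- |Λ|^½ = (4 ln 2)^1.5 / F³
- E[m] = V · |Λ|^½ · (2π)^-2 · (z² − 1) · exp(−z²/2)
- β = (Γ(2.5) · E[m] / (V · Φ(−z)))^(2/3)
- P(size ≥ k) = exp(−β · k^(2/3))
- corrected p = 1 − exp(−E[m] · P)

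Take V = 1,499,472 mm³ and F = 9.8 mm (noise of 4 mm FWHM plus the kernel: √(4² + 9²) ≈ 9.8), so |Λ|^½ = 0.0049 per mm³.

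- z = 2.3: Φ(−z) = 0.0107, E[m] = 56.8, β = 0.0280. Corrected p = 0.05 needs P = −ln(0.95)/56.8 = 0.00090, so k ≈ (7.01/0.0280)^1.5 ≈ 4,000 mm³.
- z = 3.1: Φ(−z) = 0.00097, E[m] = 13.1, β = 0.0525, P = 0.0039, so k ≈ (5.55/0.0525)^1.5 ≈ 1,100 mm³.

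At 2.3 a declared cluster must therefore be nearly four times as large, and its null probability depends more on long-range correlation.

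**2. Is 0.05 held when the assumption is true?** Simulation B: 2,000 null Gaussian fields per case, each scored in both directions; family-wise error is the share of one-directional maps with any cluster at or above k. Gaussian autocorrelation gave 0.021 and 0.022 at Z > 2.3, and 0.022 and 0.030 at Z > 3.1. A 2 mm grid gave 0.020 and 0.022 at Z > 2.3. So the level is held, conservatively.

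**3. Long-tailed autocorrelation.** The noise mixes a short-range Gaussian part (weight a) with an exponential part (weight 1 − a, decay c mm); the 9 mm kernel is then applied. One direction, 1,200 to 2,000 fields per case:

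| a | c (mm) | Z > 2.3 | Z > 3.1 |
|---|---|---|---|
| 0.95 | 5 | 0.041 | 0.027 |
| 0.98 | 10 | 0.057 | 0.034 |
| 0.80 | 5 | 0.065 | 0.047 |
| 0.50 | 5 | 0.069 | 0.048 |
| 0.95 | 10 | 0.111 | 0.049 |
| 0.50 | 10 | 0.116 | 0.061 |
| 0.90 | 10 | 0.146 | 0.060 |
| 0.80 | 15 | 0.181 | 0.072 |
| 0.90 | 20 | 0.219 | 0.074 |

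Monte Carlo standard error is √(p(1 − p)/N): for 0.111 with N = 2,400 maps it is 0.006.

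The weights are those before smoothing. The kernel removes short-range variance much faster than long-range: at a = 0.95, c = 10 it keeps about (16/97)^1.5 = 0.067 of the Gaussian part and about 0.45 of the exponential part. The tail's share afterwards is 0.05 × 0.45 / (0.05 × 0.45 + 0.95 × 0.067) = 0.0225/0.0862 ≈ 0.26, with a correlation of about 0.07 at 20 mm.

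**4. The same check with the trial's one-sample t.** Simulation A: 29 fields per data set, t converted to Z, smoothness estimated from residuals, 1,362 to 1,425 data sets per case. At Z > 2.3: 1.8% with white raw noise, and 9.6%, 12.2% and 10.8% under three long-tailed cases. At Z > 3.1: 1.0%, 5.1%, 5.7% and 5.3%. A further n = 29 run of 220 data sets per case gave about 2% with white noise and about 8% to 14% with long tails at Z > 2.3, and about 5% to 7% or less at Z > 3.1.

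**5. Not covered.** The regression maps, intensity normalization, the white-matter nuisance regressor and physiological noise removal were not simulated. The Data Analysis text specifies two-tailed 0.05 in general, but the plan does not say how the cluster maps handle direction. Two independent directions at 0.05 each would give 1 − 0.95² = 0.0975 nominally.

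**The case against.** The strongest reply is that nothing in the documents shows the level is exceeded. If the noise is near-Gaussian, the rule is conservative (about 2%), and several long-tailed cases lie close to nominal (4.1%, 5.7%, 6.5%, 6.9%). A reader might infer from the simulations that this trial's error rate is about double the stated 0.05, or that noise clusters do pass more often than stated. The documents support neither, since they report no autocorrelation, effective smoothness or mask volume. The long-tailed cases in simulation A are also severe: the kernel keeps about 1.1% of white variance but 38% to 58% of exponential variance, so after smoothing the tail is 90% to 98% of the field. Those cases show that inflation is possible, not how likely it is. The denoising steps left out could also change long-range correlation. All of this stands.

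A reader might also infer that the threshold was relaxed from a stricter one. No earlier value is stated; the wording shows only that sample size was offered as a reason, together with precedent. That the method is parametric is likewise a reading, though a well-supported one, of the Gaussianized statistic images and the reference cited for the correction.

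Finally, the plan calls the study a proof-of-concept pilot, its sample size text disclaims power for efficacy, and the one-sample map pools both arms and tests no intervention effect. That supports exploratory reporting. It does not support an unqualified corrected p = 0.05 when the condition behind it is unchecked.

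**Conclusion.** The point holds in conditional form. Neither limited sample size nor precedent establishes that the 0.05 cluster level holds at Z > 2.3 in these data, and the only multiplicity control in the updated plan rests on an assumption that it does not check. For one-directional null maps, the family-wise error is about 2% under near-Gaussian autocorrelation and about 4% to 22% under the long-tailed forms assumed here. At Z > 3.1 the same long-tailed forms give about 3% to 7%, so dependence on the assumption is much weaker there but does not vanish. The range rests on assumed autocorrelations and search volumes, and on one-sample maps or smooth Gaussian fields. It is not an estimate of this trial's error rate and does not extend by calculation to the regression maps, although the same rule is applied to them.

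**What to change.** - Base the corrected p-values on permutation inference applied to the existing contrast images, with cluster or TFCE statistics at 0.05: sign-flipping for the one-sample map, which assumes symmetric errors, and permuting participants for the regressions. This does not rely on the shape of the spatial autocorrelation.
- The section is in the past tense with its final n, so the 2.3 analysis appears already to have been run. Keep it on record, report it alongside, and label clusters that appear only at parametric Z > 2.3 as exploratory.
- If parametric inference is kept, add a sensitivity analysis at a stricter threshold such as Z > 3.1.
- Do not present small sample size as a justification for the threshold.
- State whether each map is tested in one direction or two.

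The cost is hours of computing and a few sentences of SAP text; no new data are needed. The downside is that fewer clusters may survive.

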Second, we propose that SAV will engage different aspects of the corticostriatal circuits. SAV is traditionally a non-mindful cognitive strategy that promotes positive emotions through focused attention on pleasurable thoughts or sensory experiences.⁶⁰⁻⁶² Importantly, positive emotions are linked to activity within two other critical corticostriatal structures: the ventromedial prefrontal cortex (vmPFC), which is associated with the regulation of positive emotions⁶³⁻⁶⁶, and the nucleus accumbens (NAc), which is associated with reward valuation in human and animal studies.⁶⁷⁻⁶⁹ Indeed Speer et al.⁷⁰ showed that NAc and vmPFC function were significantly augmented during a basic savoring task, and NAc function correlated with the experience of positive emotions.

We plan to use these data to inform a follow-up study in which we combine MB and SAV and determine whether the combination optimizes the engagement of corticostriatal circuits during noxious stimulation.

4. Study Procedures

- a. Study design, including the sequence and timing of study procedures (distinguish research procedures from those that are part of routine care).

Overview of Study

We aim to demonstrate that MB promotes lOFC and putamen activation and SAV promotes NAc and vmPFC activation during noxious thermal stimulation among RA patients. We will execute a randomized controlled trial (RCT) comparing two arms: SAV, and sham MB in 40 RA patients (n = 20 per group). Originally, we also randomized participants to a third arm (MB). However, due to the disruption of the COVID-19 pandemic, we will no longer randomize to MB, in order to optimize our ability to complete the project on budget. The screening and intervention sessions will take place either via secure remote video conference (e.g., Zoom), or at Johns Hopkins Bayview Medical Center, as dictated by fluid laboratory density needs and participant safety precautions. There will also be a post-intervention fMRI task, which will take place at University of Maryland-Baltimore (UMB). The fMRI visit is the only that will take place at UMB.

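### The updated imaging plan names no test in the nucleus accumbens, and its cluster-extent rule at 2.3 would usually miss a focal effect there if the search is whole-brain

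*Combined protocol and SAP*

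**What the plan says.** Section 4a (Overview of Study) names the regions for the savoring hypothesis: "SAV promotes NAc and vmPFC activation during noxious thermal stimulation". Section 7a makes corticostriatal brain function the primary outcome.

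Section 7c then prints two analysis plans.

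- **Data Analysis.** "regional signal changes in a priori regions (lOFC, putamen, vmPFC, and NAc) are assessed in first level", with statistic images "cluster thresholded to correct for multiple comparisons across brain voxels". The primary strategy follows: "We will test regional signal change in each ROI using mixed effects models", with the HEAT × PRACTICE × CONDITION interaction as the key term. CONDITION still has MB as a level.
- **Updated Statistical Approach due to Covid-19.** This says that a new plan was developed after the MB arm was dropped. Images are "smoothed with a 9mm full-width half maximum (FWHM) Gaussian kernel". A one-sample t-test (n = 29) "was used to determine whole-brain, pain-related regions", and multiple regressions relate blood flow to pain ratings. The significance rule is "we set voxelwise threshold to 2.3, cluster corrected at" p = 0.05, justified by the limited sample size.

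The updated text names no region of interest, mask or small-volume correction and states no SAV-versus-sham contrast. It does not say whether the region-level models are withdrawn.

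**The concern.** A cluster-extent test rewards wide activation. Its minimum cluster size grows as the forming threshold falls and as the images become smoother. The updated plan combines a low threshold with a 9 mm kernel, while one of the two savoring targets is a very small structure. The reason given for the threshold, a limited sample, therefore works against that target.

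Two misreadings could follow. A map with no NAc cluster could be taken as evidence against the savoring hypothesis when the rule had little chance of finding a focal effect. A surviving cluster that overlaps the NAc could be reported as NAc activation although most of it lies elsewhere.

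**Working it through.** **The plan's own figure.** The only computed design figure is n = 17 per group for over 80% power. It cannot be reproduced: the contrast map, smoothness and threshold entered in the software are not given, and the pilot contrast was MB versus sham (OFC and putamen), not savoring. For orientation, a plain two-group comparison at two-sided 0.05 gives d = (1.960 + 0.842) × √(2/17) = 0.96 (0.99 with the t distribution).

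**Inputs from section 7c.** Threshold u = 2.3, read as Z; corrected cluster level 0.05; applied smoothing 9 mm. If 2.3 is a t value on 27–28 degrees of freedom, Z is about 2.18 and the critical extent is larger.

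**Assumptions, not in the documents.** Search volume V = 1.0–1.8 litres; effective smoothness F = 9–12 mm (the applied kernel taken as a lower bound); NAc 0.4–1.0 cm³ per side.

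**Critical extent (Gaussian random field, 3D term).**

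- Expected clusters: E[m] = V × (2π)^-2 × (4 ln 2)^1.5 × F^-3 × (u² − 1) × exp(−u²/2)
- Shape: β = [Γ(2.5) × E[m] / (V × Φ(−u))]^(2/3)
- Solve 1 − exp(−E[m] × exp(−β k^(2/3))) = 0.05 for k

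Example: V = 1.4 × 10^6 mm³ and F = 9 give E[m] = 68.4, β = 0.0332, k = 3,187 mm³.

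| F | V = 1.0 L | V = 1.2 L | V = 1.8 L |
|---|---|---|---|
| 9 mm | 2,966 mm³ | 3,085 mm³ | 3,355 mm³ |
| 12 mm | 5,746 mm³ | 6,010 mm³ | 6,611 mm³ |

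At Z = 3.1 and 9 mm the extent is only about 850–940 mm³ (V = 1.2–1.8 L), so the low threshold drives the result. A simulation of null fields (500 fields, V = 1.5 L) gave 2.7 cm³ at 9 mm and 4.4 cm³ at 11 mm, against 3.2 and 5.2 from the formula.

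**Ratio to the NAc.** One side: 3.0/1.0 = 3 to 6.6/0.4 = 16.5. Both sides together: 3.0/2.0 = 1.5 to 6.6/0.8 = 8.

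**Reach of a focal effect.** A spherical NAc effect smoothed at 9 mm and peaking at Z = 4–5 covers about 0.4–1.0 cm³ above 2.3. Without noise, one side would need a peak Z of about 12–22 to fill 3.0–3.4 cm³.

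**With noise.** Proportion of simulated maps declared significant (200 fields per cell, V = 1.5 L; range over NAc 0.5 and 1.0 cm³ per side):

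| Peak Z | 9 mm, one side | 9 mm, both | 11 mm, one side | 11 mm, both |
|---|---|---|---|---|
| 3 | 2–3.5% | 4–4.5% | 1–1.5% | 1.5–4.5% |
| 4 | 2.5–7% | 8.5–18% | 0.5–2% | 3.5–10% |
| 5 | 6.5–8.5% | 20.5–30% | 1–3% | 6–14% |

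The simulation error at 18% is √(0.18 × 0.82/200) = 2.7 percentage points. For 15 versus 14 participants, Z = 4 corresponds to a standardised difference of about 4 × √(1/15 + 1/14) = 1.5, a large effect.

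**Comparison with a regional mean.** On the same smoothed images, the mean over a correctly placed NAc region (normal approximation) has about 95% power at Z = 4 with two-sided 0.05, and 86–87% at 0.05/4 = 0.0125. At Z = 3 the figures are 76–78% and 57–59%.

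**Localisation.** A surviving cluster of at least 3.0 cm³ lies at least 1 − 1.0/3.0 = 67% outside one NAc.

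**The case against.** The strongest reply is that the region-level models are still printed in section 7c as the primary strategy and are not expressly withdrawn. If they govern, the NAc has its own test and the cluster rule is secondary. That stands as a condition on this point. It does not remove the defect: those models keep MB as a level of CONDITION and come just before a section that announces a new plan. The reader cannot tell which applies.

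Four further limits stand.

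- A reader might infer that a focal NAc effect cannot reach significance. The peak Z of 12–22 is a noise-free figure. With noise, detection is low but not zero: up to 30% at Z = 5 if bilateral, and higher for stronger effects.
- In the updated section, whole-brain describes only the one-sample test. For the regressions it is inferred from the absence of any smaller volume; the reference to brain voxels belongs to the older text.
- The ratios depend on NAc volume, search volume and effective smoothness, none of which is documented. Counting both sides at 1.0 cm³ each brings the ratio down to 1.5.
- A reader might infer that Objective 2 is unanswerable. It asks about corticostriatal circuits, and the NAc is one of two savoring regions. Nothing here shows that an effect in the vmPFC would be missed.

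The missing SAV-versus-sham contrast is arguably the larger gap in the updated section, and the threshold adds to it.

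**Conclusion.** The concern holds in a limited form. The updated plan states no test in the hypothesised regions. On a whole-brain search its rule requires about 3.0–3.4 cm³ at 9 mm effective smoothness and 5.7–6.6 cm³ at 12 mm, several times one NAc under the stated assumptions. A focal NAc effect is therefore very unlikely to be declared significant, although an NAc regional mean on the same images would usually detect it at Z = 4.

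The documents do not support saying that detection is impossible, that the region-level tests have been abandoned, or that the whole savoring objective fails. The conclusion concerns the NAc part of the hypothesis and depends on the whole-brain reading and the assumed volumes and smoothness.

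**What to change.** Amend section 7c to:

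1. State that the region-level mixed models under Data Analysis remain the primary test, with CONDITION reduced to SAV versus Sham MB and HEAT × PRACTICE × CONDITION as the deciding term.
2. Apply them to mean blood flow in fixed anatomical NAc and vmPFC masks, extracted from unsmoothed images. On 9 mm images about 66–81% of the weight of an NAc mask mean comes from outside the mask (spherical masks of 0.3–0.9 cm³), so smoothed extraction would bring back the localisation problem.
3. Specify multiplicity control across the regions tested.
4. Label the cluster maps exploratory, and state the search volume and whether 2.3 is Z or t.
5. State that absence of an NAc cluster is not evidence against the hypothesis.

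**Cost.** Revised wording and a re-run on existing images; no new data. Whole-brain maps lose confirmatory status. Unsmoothed blood flow in a small region is noisier, and the 95% benchmark was computed on smoothed images, so it does not predict power for the unsmoothed test.

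The updated section already reports the n = 29 analysis in the past tense, so any regional test that departs from the printed specification must be labelled post hoc. That includes unsmoothed extraction, since the Data Analysis text smooths before assessing regional signal, and the choice of masks, which it does not define. Reporting the smoothed regional mean alongside would show whether this matters.
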